Dysphagia (swallowing impairment) involves two primary concerns: 1) the ability to swallow safely, without material entering the airway; 2) the ability to swallow efficiently, without leaving residue behind in the pockets of the pharynx. Impaired swallowing safety is linked to pneumonia while impaired efficiency contributes to risk of malnutrition. Dysphagia is common in patients with head and neck cancer prior to, and as a result of treatment. Radiation treatment for the cancer can cause and exacerbate symptoms of dysphagia. Due to an increase in the prevalence of oropharyngeal cancers secondary to the Human Papilloma Virus (HPV), a growing number of individuals are receiving radiation treatment for their disease. However, because of the typically young age at diagnosis, these individuals can expect longer post-treatment lifespans during which there is a significant chance for negative sequelae to develop, including dysphagia. When a person presents with dysphagia, a common intervention is to alter the consistency of the foods and fluids they consume. However, we lack evidence to guide the modification of food and liquid textures for clinical benefit. In particular, we lack studies demonstrating the effect of texture modification as an intervention in the head and neck cancer population. In this study, we propose to measure the flow of thin, slightly thick and mildly thick liquids in patients who have completed radiation treatment for base of tongue cancer, to understand whether or not thickened liquids provide benefit.

We have three specific aims:

Aim 1: To determine whether slightly-thick and mildly-thick liquids are palatable and acceptable to patients with base of tongue cancer. We will collect palatability measures for starch- and gum-thickened liquids with slightly-thick and mildly-thick consistencies, as defined by the International Dysphagia Diet Standardisation Initiative syringe flow test. We will also collect baseline quality of life measures to understand the impact of swallowing impairment on the participant's quality of life. Following a videofluoroscopy swallowing assessment (described under Aim 2), participants will be advised to use thickened liquids that are effective for improving their swallowing. A follow-up phone call will monitor compliance and acceptance of this recommendation. Significance: This will determine how likely participants are to adhere to a thickener recommended based on its efficacy to reduce aspiration.

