(Nestlé Resource® ThickenUp® and ThickenUp Clear®). All stimuli will be prepared in the Swallowing Rehabilitation Research Laboratory not longer than 6 hours prior to scheduled use, according to a strict standard operating procedure (refer to additional reference documents). Following preparation, stimuli will be stored in the swallowing lab until needed. Barium stimuli will be transported to the radiology suite at Toronto General Hospital in a cooler, as per routine clinical procedures.

Data to be collected from each participant:

The following types of data will be collected from participants:

- a) An intake questionnaire noting age, sex, ethnicity and race data and confirming eligibility based on the absence of reported exclusion criteria.
- b) During the intake process, we will review a list of conditions that could alter the results of the research study and identify whether any of these conditions apply. This will include disclosing the use of any medications that the participant is currently taking, in order to allow us to control for the possible influence of medication on oral sensory and motor function. Medications do not qualify as the basis for exclusion. However, it is important for us to collect information regarding the use of benzodiazepines and neuroleptic medications that are known to have possible effects on swallowing, particularly with respect to causing xerostomia (dry mouth).
- c) Palatability ratings for thickened liquids (with barium and without barium).
- d) The MD Anderson Dysphagia Inventory (a quality of life scale related to dysphagia)
- e) The Performance Status Scale – Head and Neck (a scale capturing dysphagia and diet status)
- f) The University of Washington Quality of Life Revised Version 4 (UW-WOL-R4).
- g) Tongue-pressure waveform data, collected at the anterior, middle and posterior palate using the 3-bulb tongue-pressure bulb array of the KayPENTAX Swallowing Signals Lab. If the participant is unable to tolerate the attachment of the sensors, we will measure tongue strength using the Iowa Oral Performance Instrument (IOPI). This approach does not include adhered attachments to the oral mucosa.
- h) A measure of stimulated saliva (the Saxon Test), using a 2x2 inch of folded gauze that is chewed for 2 minutes, expectorated and then weighed prior to being discarded.
- i) A videofluoroscopy recording of swallowing collected at a pulse rate of 30 pulses per second and video capture at 30 frames per second.

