- j) Responses to follow-up phone calls exploring acceptance of thickened liquids.

Data Collection Procedures: Data Collection Session 1: The participant will arrive at the lab and will be asked to complete two questionnaires: the MD Anderson Dysphagia Inventory (MDADI), the Performance Status Scale for Head and Neck Cancer (PSS-HN) and the University of Washington Quality of Life Revised Version 4 (UW-WOL-R4).

Prior to data collection, saliva flow will be collected using the Saxon Test, for which the participant will chew on folded sterile gauze for 2 minutes. The gauze will be weighed before and after chewing to determine amount of saliva production. The participant will then be asked to swallow 6 non-barium

stimuli, and 2 barium stimuli thickened using starch and xanthan-gum based thickeners. After the participant has sampled each stimulus, they will be asked to rate palatability on a visual, hedonic scale (see study instruments provided).

Data Collection Session 2: Prior to data collection, saliva flow will be collected using the Saxon Test, for which the participant will chew on folded sterile gauze for 2 minutes. The gauze will be weighed before and after chewing to determine amount of saliva production. The participant will then be seated in the videofluoroscopy suite for tongue pressure sensor attachment. A silicon strip housing three 8 mm diameter pressure bulbs will be attached in midline to the roof of the participant's mouth, with the front sensor located immediately behind the participant's upper incisor teeth. The sensor strip will be attached using a medical adhesive (Stomahesive®, Convatec, St-Laurent, Quebec, Canada).

Following sensor attachment, the video output line from the fluoroscopy unit and the tongue pressure sensors will then be connected to the KayPENTAX Digital Swallowing Workstation Swallowing Signals Lab equipment, which is located on a properly insulated cart with an uninterrupted power supply and isolation transformer (see Image 1). If the participant is unable to tolerate the attachment of the sensors due to mucositis or general discomfort, we will measure tongue strength using the Iowa Oral Performance Instrument (IOPI) and collect the videofluoroscopy measures without the use of the adhered sensors.

Image 1. Tongue pressure sensors.

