Participants will be asked to swallow a series of thin, slightly-thick and mildly-thick barium stimuli 1 (3 boluses each of 5 stimuli, for a total of 15 boluses) in videofluoroscopy, with concurrent measurement of tongue-palate pressure. Videofluoroscopy will be performed at optimal temporal resolution (30 pulses/second) and captured at 30 frames/second. The stimuli will be presented in a randomized design, blocked by stimulus type. Participants will be allowed to take natural sized sips of each stimulus from cups containing 40 ml. Sip volume and mass will be calculated, by weighing the cups prior to and after the videofluoroscopic assessment.

Data Processing:

The tongue-pressure waveform will be segmented using an automatic segmentation algorithm developed previously in the PI's lab. Similarly, the videofluoroscopy recordings will be spliced into single bolus clips and the audio channel will be muted to remove cues that might bias rating. Blinded videofluoroscopy rating will then be performed in duplicate by trained raters in the [name] Lab following established procedures (see SOP provided as an additional study document). Discrepancies between raters will be flagged and resolved at consensus meetings, as required. These procedures will yield a

large number of parameters for each swallow. We will use established measures within our lab to collect and analyze measures related to kinematics and residue.

[figure not shown]
Follow-up phone calls: If deemed appropriate, the participant may be offered the opportunity to complete a follow-up component. For those willing to participate, this optional experiment will involve two follow-up telephone calls (at 2 weeks and 3 months following the videofluoroscopy) to determine compliance with use of thickened liquids recommended following the videofluoroscopy (see study instruments provided for questionnaires).

Data Analysis:

For Aim 1, we will compare hedonic ratings for the different stimuli using a univariate ANOVA. It is hypothesized that ratings will be significantly better for the thin and slightly thick stimuli compared to the mildly-thick stimuli, and that a preference will be seen for the gum compared to the starch thickened liquids.

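### Aim 1's palatability hypothesis needs ratings of thin liquid that the plan does not list, and its ANOVA does not say how barium and non-barium ratings are kept apart

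*Combined protocol and SAP*

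**What the plan says.** - **Aim 1 (Section 2)** sets the scope of the ratings: "We will collect palatability measures for starch- and gum-thickened liquids with slightly-thick and mildly-thick consistencies". Thin is not named.
- **Data to be collected, item (c) (Section 3)** repeats that scope: "Palatability ratings for thickened liquids (with barium and without barium".
- **Data Collection Session 1 (Section 3)** gives the counts: "The participant will then be asked to swallow 6 non-barium" "stimuli, and 2 barium stimuli thickened using starch and xanthan-gum based thickeners". It then has every sample rated: "After the participant has sampled each stimulus, they will be asked to rate palatability on a visual, hedonic scale". It gives no consistency for any of the eight samples and no order.
- **Data Analysis (Section 3)** gives the test: "For Aim 1, we will compare hedonic ratings for the different stimuli using a univariate ANOVA". The hypothesis is that "ratings will be significantly better for the thin and slightly thick stimuli compared to the mildly-thick stimuli", with gum also preferred to starch.
- **Stimuli (Section 3)** says that the array developed for the study includes thin liquids. The non-barium samples are made from lemon-flavoured water; the barium stimuli for videofluoroscopy contain 20% w/v barium.
- **Session 2 (Section 3)**, by contrast, names thin, gives five stimuli with three boluses each, and states a randomised design blocked by stimulus type.

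**The concern.** The hypothesis has thin on one side of a comparison, while the two places that define the palatability data leave thin out. If the Session 1 sheet follows those definitions, the thin versus mildly-thick comparison cannot be made.

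The second problem is barium. The hypothesis concerns consistency and thickener only, yet two of the eight rated samples have a different base that may well taste different. If the ANOVA groups ratings by consistency, any dislike of barium is counted against whichever consistency the barium samples have. A finding that mildly-thick is rated worse could then partly reflect barium, or a true difference could be hidden. An unstated tasting order leaves room for a similar mix-up with sequence effects.

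This ANOVA is the only stated quantitative test of palatability. It also carries the starch versus gum preference, because the Aim 3 analysis is described as qualitative. With 10-12 participants, a thin sample that was never rated cannot be recovered after Session 1.

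**Working it through.** **1. Counting cells.** Two thickeners × two consistencies = 4 thickened cells; with thin, 4 + 1 = 5. Session 2 agrees with this: 5 stimuli × 3 boluses = 15, the plan's own total. Session 1 has 6 non-barium samples, which is neither 4 nor 5, so there must be a repeat or an unlisted item. Six is enough to hold all five cells.

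**2. What the wording allows.** Assume that the six non-barium samples come from the five cells, with repeats allowed, and that the barium pair is one starch and one gum, each slightly- or mildly-thick.

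- Possible compositions: C(10,6) × 2 × 2 = 210 × 4 = 840.
- Compositions without thin: C(9,6) × 4 = 84 × 4 = 336. In these the thin contrast cannot be estimated.
- Compositions with all five non-barium cells: 5 choices of repeated cell × 4 = 20.
- By enumeration, a further 144 contain thin but leave mild-thin or mild-slight not estimable even with a barium term, for example when mildly-thick is given only with barium.

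These counts show what the text permits. They are not probabilities.

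**3. Bias if ratings are pooled by consistency.** Let b be the change in rating caused by the barium base, negative if barium is disliked. The documents give no value for b. Take all five non-barium cells as present, with the sixth sample a repeat of thin or outside the five cells. Thin then has no barium sample, and each thickened consistency has two non-barium samples plus its barium samples. The shift in a consistency mean is (number of barium samples × b) / (all samples of that consistency).

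| Barium pair | Shift, slightly-thick | Shift, mildly-thick | Bias in mild-thin | Bias in mild-slight |
|---|---|---|---|---|
| Both mildly-thick | 0 | 2b/4 = b/2 | b/2 | b/2 |
| Both slightly-thick | 2b/4 = b/2 | 0 | 0 | -b/2 |
| One of each | b/3 | b/3 | b/3 | 0 |

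An additive model with consistency and thickener, and no barium term, gives the same biases: 0.50b, -0.50b and 0.33b. For illustration only, b = -1 with both barium samples mildly-thick lowers the mildly-thick mean by 0.5 points against both comparators.

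If the sixth sample repeats a thickened cell, the sizes change somewhat. Even so, each of the 20 compositions has at least one biased consistency contrast when pooled.

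**4. What removes the bias.** In all 20 compositions both contrasts remain estimable once a barium term is added, and that term removes the bias under the additive model. Restricting the contrasts to non-barium samples removes it without needing additivity of barium.

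**The case against.** The strongest defence is that the plan, read sensibly, already works. The Stimuli section includes thin in the array, every sampled stimulus is rated, and the hypothesis names thin, so thin is probably one of the six; item (c) may be only a loose one-line summary. An ANOVA over the different stimuli can be read as a factor with up to eight levels, in which consistency is contrasted among non-barium samples with no barium bias. The study instruments and operating procedures, which are not in these documents, may list the samples and their order. And this is a feasibility pilot.

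Much of that stands, and it rules out several stronger conclusions that a reader might draw:

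- *That 6 + 2 samples cannot cover the design.* They cannot fill a full crossing with barium (5 + 5 = 10 cells), but the hypothesis contains no barium effect. It needs five non-barium cells, and these fit within six samples.
- *That the barium pair can represent only one consistency.* No consistency is given. One could be slightly-thick and the other mildly-thick.
- *That barium is always tasted last.* Session 1 joins the two groups with "and", which fixes no sequence. The order is simply not stated.
- *That thin is not rated, or that confounding is certain.* Neither is stated. Confounding arises only if ratings are pooled by consistency.

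What the defence does not remove is the mismatch between the hypothesis and the two definitions of the data, nor the absence of any stated contrast, barium term or within-participant structure for Aim 1. Where Session 1 cites the study instruments, it does so for the rating scale. Even if a stimulus list exists elsewhere, Aim 1 and item (c) still disagree with the hypothesis.

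**Conclusion.** The concern holds in a conditional form. It is certain from the text that the hypothesis requires thin ratings which Aim 1 and item (c) do not list, that the eight Session 1 samples and their order are unspecified, and that the analysis states neither a barium term nor a within-participant contrast.

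Bias depends on how the ANOVA is set up. If ratings are pooled by consistency, with all five non-barium cells present and the sixth sample not a repeat of a thickened cell, at least one of the two hypothesised consistency contrasts is off by b/3 or b/2 in size, and the sign depends on the barium pair. That rests on an assumed barium effect b, one starch and one gum barium sample, and additive effects. With one level per stimulus and contrasts among non-barium samples, the bias is nil.

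This should be changed before Session 1 data are collected, because the change is nearly free and the hypothesis could otherwise be untestable in part or biased.

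**What to change.** 1. **Reconcile the text.** Name thin among the rated liquids in Aim 1 and item (c), to match the hypothesis. List the Session 1 samples, and make sure the six non-barium ones include thin, slightly-thick starch, slightly-thick gum, mildly-thick starch and mildly-thick gum. Say what the sixth is, and give the consistency of each barium sample.
2. **State the analysis.** Test the consistency and thickener hypotheses within participant on the non-barium samples only, or add a barium term. Compare each barium sample only with its non-barium match of the same thickener and consistency.
3. **Randomise the Session 1 tasting order** and record it. Session 2 already states a randomised design.

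Cost: protocol wording and an order sheet, with no extra samples or visits. The downside is that, if the contrasts are restricted to non-barium samples, the barium ratings no longer add to the main contrasts.

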- Participants who do not show impaired swallowing safety on thin liquids in the videofluoroscopy (Penetration Aspiration Scale scores of 1 and 2) will be withdrawn from the study.
- Participants who have had, or have a planned neck dissection will be excluded.
- Individuals with tracheostomy *in situ* will be excluded from the study.
- Individuals with cognitive communication difficulties that preclude the understanding of the protocol or following study instructions will be excluded from the study.
- Due to the requirement to swallow stimuli containing starch based thickeners, which carry a significant carbohydrate load, individuals with Type 1 Diabetes will be excluded.
- Individuals with known allergies to latex, dental glue or barium will be excluded, due to the probability that these items will come into contact with the oral mucosa during data collection.
- Children and pregnant women will be excluded from the study due to the use of radiation
- Occupational exposure to radiation exceeding half the limit specified for Ontario exposed workers within the past 12 months.

These exclusion criteria will be confirmed using a self-report questionnaire form at the time of intake into the study (see standard operating procedures [SOP], provided as an additional study document). Any questions will be clarified through discussion with the research assistant responsible for participant intake, and, where necessary with the principal investigator.

Recruitment:

This is a preliminary study that will demonstrate feasibility for a future planned extension. We propose to recruit 10-12 participants. Potential participants will be identified by study Co-PIs [name] and [name] through the current radiation therapy clinics and base of tongue cancer caseloads at Princess Margaret Cancer Centre.

Stimuli:

An array of barium and non-barium stimuli has been developed for this study. These stimuli include thin, slightly-thick and mildly-thick liquids, defined using the International Dysphagia Diet Standardisation Initiative (IDDSI) gravity flow measures. The barium stimuli used for videofluoroscopy will be prepared using E-Z-Paque® barium in 20% w/v barium concentration with starch and gum-based thickening agents (Nestlé Resource® ThickenUp® and ThickenUp Clear®). The non-barium stimuli will be prepared using Nestle's Lemon Splash® lemon-flavoured water and the same starch and gum-based thickening agents

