For Aim 2, blinded videofluoroscopy rating will be performed in duplicate, and discrepancies between raters will be flagged and resolved at a consensus meeting. The frequency of aspiration will be explored with the thin stimuli and compared to the prevalence of aspiration when thickeners are introduced using chi-square statistics.

We will model the impact of stimulus on two timing measures of pharyngeal bolus flow from the videofluoroscopy (i.e., a) the interval from the bolus passing the mandibular ramus until laryngeal vestibular closure; b) the interval from the bolus passing the mandibular ramus until entering the upper esophageal sphincter) and on measures of post-swallow residue (Normalized Residue Ratio Scale). The Saxon test results regarding oral dryness will be used as a covariate for all analyses, as illustrated in the Figure below:

A path analysis approach will be used to first identify differences in tongue pressure across stimuli

(Question 1). If confirmed, this potential modulator will be added to the Question 2 model as a covariate (Question 3). The planned analyses will involve linear mixed model repeated measures ANOVAs with a factor of stimulus.

For Aim 3, we will use qualitative methods to describe participant reports of adherence to the prescribed thickener. Information from the quality of life and performance status scales collected in session 1 will be used to inform our understanding of variations on patterns of thickener acceptance.

4. Risks and Benefits

Risks

The following risks will be disclosed to all participants prior to obtaining their consent to participate:

- a) Participants may experience local mucosal irritation from the glue on the adhesive strip used to attach the tongue-pressure bulbs for data collection. The glue usually wears off within 90 minutes following the conclusion of data collection. In the incidence that participants are unable to tolerate the attachment of the sensors, we will use the IOPI tongue bulbs to collect tongue measurements, and collect videofluoroscopic data using the same protocol.
- b) Participants may dislike the taste or texture of some of the thickened liquid stimuli in the study. Participants will be reminded that they are free to discontinue participation at any time.

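### Aim 1 states two directional hypotheses about palatability, but the one planned ANOVA across stimuli tests neither; two prespecified within-participant contrasts would

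*Combined protocol and SAP*

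**What the plan says.** Section 3, Data Analysis, gives the Aim 1 method in one sentence: "For Aim 1, we will compare hedonic ratings for the different stimuli using a univariate ANOVA". The next sentence gives two predictions. The first is about consistency: "It is hypothesized that ratings will be significantly better for the thin and slightly thick stimuli compared to the mildly-thick stimuli". The second is about thickener: "a preference will be seen for the gum compared to the starch thickened liquids".

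The stimuli rated in Session 1 are described under Data Collection Procedures: "The participant will then be asked to swallow 6 non-barium" "stimuli, and 2 barium stimuli thickened using starch and xanthan-gum based thickeners". That makes eight, and each participant rates all of them. The document does not list which consistency and thickener each of the eight has.

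For Aim 1 the plan names no contrast, no consistency-by-thickener structure, no participant term, no follow-up test, no multiplicity rule, no alpha and no sidedness. For the Aim 2 timing, residue and tongue-pressure outcomes it plans "linear mixed model repeated measures ANOVAs with a factor of stimulus".

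Under Recruitment: "This is a preliminary study that will demonstrate feasibility for a future planned extension", and "We propose to recruit 10-12 participants". No power calculation is given.

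**The concern.** The predictions are specific and the test is not. An overall F asks whether any of the stimulus means differ. It can be significant because of a barium effect, a thickener effect, or one disliked product, with consistency playing no part. It can also miss a real consistency effect, because its power is spread over up to seven directions of difference when the hypotheses concern two.

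The contrasts would then have to be chosen after the ratings have been seen. A later, larger study needs the size of the consistency and thickener effects with their uncertainty, and an F statistic does not supply these.

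**Working it through.** The protocol has no power figure to reproduce, so the check compares two tests of the same data.

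**Inputs from the protocol.** n = 10 to 12. Number of stimuli k = 8 (all rated), 6 (non-barium only) or 5 (thin, plus two consistencies by two thickeners, which is the number used in videofluoroscopy).

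**Assumptions, because the protocol states none of them.** Two-sided 5%, a repeated-measures model with error df (k-1)(n-1), and sphericity.

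**Formulas.** For stimulus means m_j, residual SD s and contrast weights c_j:
- contrast noncentrality = n(Σc_j m_j)² / (s²Σc_j²), on 1 numerator df
- overall noncentrality = nΣ(m_j - m̄)² / s², on k-1 numerator df
- power = probability that a noncentral F exceeds the 5% critical value of the central F

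If all the variation among means lies along one contrast, the two noncentralities are equal. Only the numerator df, and so the critical value, differ.

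**Step 1: one effect real.** Set the noncentrality (NC) so that the 1-df contrast has 80% power, then put the same value into the overall F.

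| n | k | df | NC | Overall F |
|---|---|---|---|---|
| 10 | 5 | 4, 36 | 8.29 | 55.9% |
| 10 | 6 | 5, 45 | 8.20 | 51.8% |
| 10 | 8 | 7, 63 | 8.10 | 45.7% |
| 12 | 5 | 4, 44 | 8.21 | 56.5% |
| 12 | 6 | 5, 55 | 8.13 | 52.5% |
| 12 | 8 | 7, 77 | 8.05 | 46.3% |

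The loss is about 23 to 34 points. For the overall F to regain 80% would take 16 to 19 participants in place of 10, or 19 to 23 in place of 12.

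A worked case with k = 5, n = 12: let thin and both slightly-thick stimuli lie 0.75 residual SD above both mildly-thick ones. The grand mean is 0.45, so the overall noncentrality is 12 × (3 × 0.30² + 2 × 0.45²) = 12 × 0.675 = 8.1. With the three upper cells weighted equally, the contrast noncentrality is 12 × 0.75² / (1/3 + 1/2) = 8.1. Power is 80% for the contrast and 56% for the overall F.

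**Step 2: does a significant F support the consistency hypothesis?** Simulation with k = 5 (40,000 runs): only a gum-starch difference exists, sized for 80% power on its own contrast. The overall F is significant in about 56% of trials although consistency has no effect.

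**Step 3: both effects real, each with 80% contrast power.** In balanced cells the two contrasts are orthogonal, so the noncentrality doubles (for example 2 × 8.05 = 16.1 at k = 8, n = 12). The overall F then has 88% (k = 5), 85-86% (k = 6) or 81% (k = 8). What remains for each hypothesis depends on the unnamed follow-up. In simulation with k = 5, a contrast tested only after a significant F keeps about 76%; a Scheffé follow-up gives about 37-38%.

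**Step 4: the cost of testing two contrasts.** At the stricter Holm step (2.5%), 80% becomes 70-71% with pooled error. On contrast-specific error with n-1 df, it becomes 58-59% at n = 10 and 61-62% at n = 12.

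**Step 5: the participant term.** If the Aim 1 ANOVA were a one-way analysis ignoring participant (k = 5, 20,000 runs), its type I error would be about 1.4% at a within-participant correlation of 0.3 and below 0.1% at 0.7. Its power for a 1.0 SD effect would be 53-65% and 9-12% respectively, against 74-84% for the repeated-measures F.

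**The case against.** The case against has real weight.

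- **The overall F is not said to decide anything.** The protocol neither calls it the decision test nor rules out follow-up contrasts. This stands: the defect is that no contrast is prespecified, not that contrasts are forbidden.
- **A factorial reading is possible.** Hypotheses worded by consistency and by thickener would suit a factorial ANOVA, where consistency has 2 df and 80% falls only to about 70%. That also stands, but the plan does not say it, and even a 2-df test does not show the predicted direction.
- **The power loss is conditional.** A reader might infer that the ANOVA always wastes much of the sample. Step 3 shows otherwise when both predicted effects are real.
- **The gain after adjustment can be small.** With five stimuli, 59-62% on n-1 error df is only a few points above 56%. The comparison is somewhat uneven, since the 56% itself relies on sphericity.
- **This is a feasibility pilot with no power claim.** True, so false negatives are not the main issue. But the protocol does predict significant differences, and linking each prediction to a test costs nothing in a pilot.

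A reader might also extend the point to Aim 2, where five stimuli enter as one factor. The documents do not support that. Its analysis text states no one-df hypothesis; it asks about the impact of stimulus and about tongue-pressure differences across stimuli, which an overall test answers. Nor are the five stimuli a single ordered scale, because consistency is crossed with thickener. Replacing that test by contrasts against thin could lose power. With n = 12, suppose only mildly-thick differs and its contrast with thin has 80% unadjusted power. The overall noncentrality is then 8.21 × 1.5 × 1.2 = 14.8 (1.5 is the contrast's sum of squared weights; 1.2 is the sum of squared deviations per squared unit difference). The overall F has 85%, against 71% for the contrast at 2.5%.

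**Conclusion.** The point holds for Aim 1. Two directional hypotheses are stated, the only planned test is one ANOVA across stimuli, and a significant F would support neither. This mismatch is read from the text and needs no assumption.

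The power loss is secondary and conditional: 80% falls to 46-56% if just one effect is real, and there is no such loss against the global null if both are. These figures rest on two-sided 5%, sphericity, a participant term in the model and effects sized to give 80% contrast power; the protocol gives none of these. The documents do not support a claim that the ANOVA loses power in general, or that Aim 2 shares the fault.

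**What to change.** For Aim 1:

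1. Fit a repeated-measures model with participant as a random effect.
2. Make two within-participant contrasts the tests of the hypotheses: (a) the mean of thin and slightly-thick minus mildly-thick, averaged over thickener; (b) gum minus starch among thickened stimuli at matched consistency.
3. Apply Holm over the two, state alpha and sidedness, report each estimate with a 95% confidence interval, and keep the overall F as descriptive.
4. State the weights in (a), and how the six non-barium and two barium stimuli enter. Giving thin and slightly-thick half the weight each raises the sum of squared weights from 0.833 to 1/4 + 1/8 + 1/2 = 0.875. In the worked case the noncentrality becomes 12 × 0.5625 / 0.875 = 7.7 and power is 78% in place of 80%.
5. Say whether the consistency hypothesis is the pooled claim. If it means that thin and slightly-thick each exceed mildly-thick, the pooled contrast does not establish both, and two pairwise contrasts are needed.

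For Aim 2, keep the overall stimulus test and report estimates against thin with 95% confidence intervals beside it.

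The cost is a few sentences of analysis text, with no change to data, visits or participants. The downsides are that patterns outside the two contrasts become descriptive and that the Holm step costs the power shown in Step 4.
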